t-PA Prophylaxis to Reduce Central Venous Catheter Associated
Infection and Thrombosis (TOPCAT)

NCT03672006

February 5, 2019

INSTITUTIONAL REVIEW BOARD SUMMARY

PRINCIPAL INVESTIGATOR: [name]

STUDY TITLE: t-PA Prophylaxis to reduce Central Venous Catheter Associated Infection and Thrombosis (TopCAT)

A. PURPOSE OF THE STUDY

The purpose of this pilot study is to test feasibility of concept, consent and enrollment rates, and mechanics of study designed to assess if intra-catheter dwells of tissue plasminogen activator (t-PA: Alteplase; Activase®, Genentech) is effective in decreasing the rate of clinically diagnosed central line associated blood stream infection (CLABSI) or venous thromboembolism (VTE) in central venous catheters (CVC) compared to standard of care heparin dwell.

B. HYPOTHESIS / SPECIFIC AIMS

We hypothesize there will be a lower rate of CLABSI or VTE in CVCs who receive t-PA as a dwell medication.

We will test this hypothesis in the following aims:

Aim 1: It is feasible to enroll patients with CVC and randomize to receive t-PA vs heparin dwell.

- Determine number of eligible patients, consents rates, and adherence to study protocol in patients with CVC in the CHW Intensive Care Unit (ICU).

- Calculate the number of centers needed to adequately power a multi-center trial to determine if t-PA is effective in reducing CVC complications from the rates found in this pilot study.

Aim 2: Compare the rate of VTE and CLABSI in patients with a CVC in the ICU randomized to receive t-PA vs. heparin as a dwell in the CVC.

- This will be a prospective, blinded, RCT enrolling 20 patients in the ICU with a CVC to receive t-PA or heparin to dwell for a minimum of 30 minutes every three days until CVC removal, discharge from the ICU or a maximum of 10 doses have been received.

C. BACKGROUND, SIGNIFICANCE, AND RATIONALE

Central line associated blood stream infection (CLABSI) and venous thromboembolism (VTE) continue to be a major source of morbidity in patients with central venous catheter (CVC). There is physiologic plausibility that by decreasing fibrin development with the use of t-PA in CVCs, the rate of CVC-associated VTE and CLABSI would be decreased.

It is well established that t-PA is safe and effective in restoring CVC patency after occlusion in adults (Deitcher 2002, Ponc 2001) and children (Blaney 2006), and is FDA approved for this use in both adults and children. Using t-PA for occluded CVC is standard of care in CHW PICU and is recommended by clinical practice standards, including Infusion Nurses Society (INS), Association for Vascular Access (AVA), American Association of Critical Care Nurses (AACN), Oncology Nursing Society (ONS).

It is not known if t-PA would be effective in preventing fibrin deposition and subsequent complications of VTE and CLABSI if administered prophylactically. Analysis of prophylactic t-PA used as a dwell solution for dialysis catheters suggests that this may be the case. A meta-analysis (Firwana 2011) reviewing randomized controlled trials of t-PA as a preventative locking solution for hemodialysis catheters compared to heparin found a decrease adverse events including thrombosis with the use of t-PA (Schenk 2000, Hemmelgarn 2011, Gittins 2007).

Use of t-PA for preventing VTE and CLABSI in the non-dialysis catheter is very limited. Preliminary evidence in pediatric patients with long term CVC dependency has shown that prophylactic dwell of tissue plasminogen activator (t-PA) has decreased episodes of CVC dysfunction; however, that study was underpowered to test the outcomes of CLABSI or VTE (Malec 2017). A multicenter study would be needed to provide sufficient sample size. The pilot study proposed here will test feasibility of concept, enrollment and consent rates, and mechanics of study design to be used to inform a grant application for a future multicenter trial.

Currently, heparin as a capping or locking solution is the standard of care for functioning CVCs at CHW with t-PA reserved for restoration of flow with occluded CVC.

D. DESIGN AND METHODS

This pilot study at CHW will be a prospective, blinded, RCT enrolling 20 patients in the PICU with a CVC to receive t-PA (study drug) or heparin (current standard of care and defined as control arm for this study) to dwell for a minimum of 30 minutes every three days until catheter removal or discharge from the PICU. Primary outcomes would be CLABSI or VTE. Secondary outcomes would be episodes of CVC dysfunction, off study use of t-PA, and bleeding.

Patients meeting the following criteria will be eligible for study participation

Inclusion criteria:

- Age >2 weeks(corrected for gestational age) to ≤ 18 years old

- PICU admission
- CVC placed within 72 hours of enrollment (tunneled such as PICC, Broviac or Hickman, or untunneled) and in place during hospitalization

Exclusion criteria:

- Pregnancy
- Non-English-speaking subjects and/or parent/guardian
- Platelet count < 20,000
- Active CVC infection-defined as positive blood culture from the in -situ CVC at time of enrollment
- Current radiographically confirmed VTE
- Currently receiving treatment doses of anticoagulation (heparin infusion >15U/kg/hr, enoxaparin injections \geq 2mg/kg/day or \geq 60mg/day)
- CVC diameter <1.9 Fr
- Current or previous diagnosis of Heparin Induced Thrombocytopenia or allergy to heparin or t-PA
- Med-a-port catheters
- Active internal bleeding
- Recent intracranial or intraspinal surgery
- Serious head trauma
- Intracranial conditions that may increase the risk of bleeding
- Bleeding diathesis
- Current severe uncontrolled hypertension

Any patient admitted to the ICU and meeting the above inclusion criteria will be approached for consent within 72 hours CVC placement. Randomization and administration of t-PA/heparin control treatment will be initiated within 24 hours of enrollment.

After 1:1 randomization, t-PA/heparin will be infused in the CVC for a dwell duration of 30 minutes-4 hours and then withdrawn (lock therapy) every 3 days until discharge from the PICU, CVC removal or a maximum of 10 doses received. Additional lumens will be treated on subsequent days. Any lumen requiring continuous infusion of vaso-active medication will not receive dwell therapy, evaluated on a day-to-day basis. Timing of instillation of study dwell medication will be adjusted so as not to interfere with medications for patient care. Other stopping points of t-PA treatment are in Section L.

E. TOTAL NUMBER OF HUMAN RESEARCH PARTICIPANTS PROPOSED FOR THIS STUDY AT THIS SITE AND GLOBALLY. WHAT ARE THESE NUMBERS BASED ON?

This single center, pilot study will enroll 20 subjects at CHW. This sample size was chosen for the ability to be internally funded and to complete pilot data collection in a timely manner, with anticipated grant submission for a multi-center study in 2020.

F. DRUGS OR PROCEDURES

Procedures to be completed for this study are as follows:

After informed consent/assent, the patient will be randomized and assigned to either the treatment arm (t-PA lock) or control arm (heparin lock). Randomization will be stratified by age (<5 or ≥5 years old). Pharmacy will blind the study medication t-PA so that it is indistinguishable from the control arm. Randomization will be done in the investigational pharmacy prior to the dispensing of the t-PA/heparin. During enrollment, the unblinded assignment log will be kept in the locked investigational room in central pharmacy.

Study Treatment and Dosing

In subjects randomized to the t-PA (Alteplase; Activase®, Genentech, 1mg/cc concentration), dosing will comply with the CHW Policy and Procedure Protocol *t-PA Administration for Central Venous Access Devices (CVAD)*; subjects randomized to the control arm, standard of care heparin group, will receive an equivalent volume for weight of heparin 10 units/ml. The bedside RN will administer the study medication/heparin as per the above protocol. The CVC should be flushed with normal saline prior to infusion of t-PA/heparin. After dwelling time of 30 minutes-4 hours, t-PA/heparin control should be withdrawn, check for blood return in CVC and flush line with normal saline as per policy. Each lumen of multi-lumen CVC should be treated every 3 days until patient discharge from ICU, removal of CVC, or a maximum of 10 doses of t-PA/heparin control are received.

Patient weight	Volume T-PA/Heparin
0-10kg	0.5ml
10-20kg	1 ml
>20kg	2 ml

These doses by body weight have been approved by the FDA for and CHHS Patient Care Protocol (tPA Administration for Central Venous Access Devices (CVADs) for use in children with CVC and are not associated with significant bleeding. If a 2mg (ml) dose of t-PA is administered by bolus injection directly into the systemic circulation, rather than as a dwell within the CVC, the drug concentration would return to endogenous levels with 30 minutes.

Ultrasound imaging

At the end of the study period, a noninvasive ultrasound with doppler will be performed for research purposes to assess for asymptomatic thrombosis in the blood vessel of the CVC location.

G. RISK CATEGORY:

Both arms of the study: Risk Level (2) 45 CFR 46.405 - Research involving greater than minimal risk but presenting the prospect of direct benefit to the individual child subjects involved in the research.

H. RISKS AND THE PRECAUTIONS WHICH WILL BE TAKEN TO MINIMIZE RISK EXPOSURE

There is a risk of bleeding at higher doses of both the study drug (t-PA) and heparin control, as both drugs used in standard clinical practice alter the coagulation system. However, the doses by body weight used in this study have been approved by the FDA for and CHW Policy *tPA Administration for CVADs* for use in children with CVC and are not associated with significant bleeding. If a 2mg (ml) dose of t-PA is administered by bolus injection directly into the systemic circulation, rather than as a dwell within the CVC, the drug concentration would return to endogenous levels with 30 minutes. As a precaution, we will monitor the dose of drug received and follow the CHW policy and procedure for administration. Both arms of the study are currently used in clinical care, it is the timing of the intervention that is under study. As additional precaution, we will exclude patients at increased risk of bleeding (platelet count < 20,000 or receiving therapeutic dosed anticoagulation).

All adverse events experiencing by study subjects will be monitored throughout the active study treatment period and for 30 days following the last dose of the t-PA/heparin, or for 7 days after CVC removal, whichever occurs first. For patients with CVC in place at time of hospital discharge, chart review will be performed to capture events up to 7 days after discharge.

Breach of Confidentiality

Data necessary for the completion of this study will be extracted from the subject electronic medical record and maintained in a REDCap database on the CTSI server. Some PHI will be maintained in this database but will only be accessible to study team members listed on the registration page. Any study information maintain on paper will be held in a locked file cabinet in the Critical Care offices.

I. PROVISION FOR THE PROTECTION OF PRIVACY OF SUBJECTS AND TO MAINTAIN THE CONFIDENTIALITY OF DATA

As of October 2017, the NIH has updated their policy on Certificates of Confidentiality and are automatically issuing these for eligible studies that are NIH funded. They no longer issue a paper certificate, nor only submit on request.

Does this study qualify for automatic issuance of a Certificate of Confidentiality by the NIH?

No Yes

The following encryption products employ cryptographic modules that the National Institute of Standards and Technology has certified as meeting FIPS 140-2 requirements. Children's Hospital and Health System endorsed the use of these products made to encrypt hard drives and removable media. All electronic research data must be encrypted using one or more of these products.

Please indicate which encryption tools you are using to secure your research data.

___ Credent Mobile Guardian (RS, PD)

- GuardianEdge Hard Disk and GuardianEdge Removable Storage Encryption (HD, RS, PD)
- IronKey encrypted flash drives (RS)
- McAfee Endpoint Encryption (HD, RS)
- Microsoft Bitlocker (HD, RS when used with Windows 7 and FIPS compliant algorithms are enabled)
- PGP Whole Disk Encryption and PGP Portable (HD, RS)
- SafeNet Protect Disk and SafeNet Protect File (HD, RS)
- Seagate Secure Self-Encrypting Drives (HD when encryption option is enabled)
- Symantec Endpoint Encryption (HD, RS, PD)
- WinMagic SecureDoc encryption (HD) (for MCW owned computers)
- Other (*add description*)

Does not apply because:

- Data is de-identified – no PHI collected (*please provide detailed information on data elements in your protocol application*)
- Data is stored on paper only
- Data is stored on CHW secured shared drives.
- Data is stored on MCW secured shared drives.

J. PROVISIONS FOR MONITORING DATA TO ENSURE THE SAFETY OF SUBJECTS; AND ADDITIONAL SAFEGUARDS TO PROTECT THE RIGHTS AND WELFARE OF SUBJECTS WHO ARE LIKELY TO BE VULNERABLE

Adverse Event Monitoring

Any patient receiving a minimum of 1 dose of the t-PA/heparin control will be followed for adverse events by the study investigators and research coordinators for 30 days following the last dose of the t-PA/heparin, or for 7 days after CVC removal, whichever occurs first. For patients with CVC in place at time of hospital discharge, chart review will be performed to capture events up to 7 days after discharge.

Adverse events will be considered any change from baseline. Expected adverse events are listed in section H; this section also includes those events considered serious but expected within this protocol. Expected SAEs will be reported in aggregate at the study’s annual review. Any SUSAR experienced during the study will be reported per IRB’s Reportable Events guidelines. At completion of the study adverse event rates between the study group and heparin control group will be compared and included in any final study reports.

Serious Adverse Events

If any subject enrolled in the study experiences any serious adverse event, the study team and care team will discuss the likely cause of the events. If it is determined that the event is probably or definitely related to the t-PA/heparin control the study treatment can be discontinued at the discretion of the care team and study team. Subjects whose treatment is discontinued will be followed for 30 days after the last t-PA/heparin control dose or until hospital discharge, whichever occurs first.

K. ANTICIPATED BENEFITS ASSOCIATED WITH THE PROTOCOL TO HUMAN RESEARCH PARTICIPANTS AND SOCIETY

Benefit to the individual patient may include a decreased risk of CVC infection or VTE.

Benefit to society at large will be knowledge gained to optimally design multicenter interventional study to develop therapy to reduce the risk of central line infection and/or thrombosis. There is evidence that these complications result in unfavorable outcomes such as increased length of mechanical ventilation, increased length of stay, increased healthcare cost, and increased mortality.

L. STOPPING POINTS THAT WOULD NOT ALLOW THE STUDY TO CONTINUE AS PROPOSED

Withdrawal from study

The PI or subject's primary care team can withdraw the subject from this study due to

- Consent is withdrawn by subject's family
- Treating physician wishes to withdrawal subject for any reason

M. IS THERE A DATA SAFETY MONITORING BOARD IN PLACE? WHO ARE IT'S MEMBERS? HOW OFTEN DO THEY MEET?

There is no DSMB planned for this study.

N. DESCRIBE HOW THE CONSENT AND ASSENT PROCESS WILL TAKE PLACE. INCLUDE A LIST OF APPROPRIATELY TRAINED PERSONNEL WHO WILL BE INVOLVED.

After an eligible subject is identified, written informed consent will be obtained in person by an investigator or coordinator listed on the registration page for this study. Study investigators who are also the eligible subject's attending physician at the time of consent will not participate in the consent conversation to remove any undue influence posed by the dual role. Following consent, a copy of the completed documents will be placed in the subject's medical record, and a second copy will be given to the subject's family. A consenting and enrollment log will be maintained by the research team for all the patients who are screened for study, approached meeting eligibility criteria of the study and who consented/ or denied participation in the study.

We are requesting a waiver of assent for patients intubated, pharmacologically sedated, cognitively delayed that they would not fully comprehend what they are consenting to, and patients too critically ill defined as reduced consciousness or impaired decision-making capacity. The decision of an individual's capability to assent for the study is made by reviewing medical records for that specific information. This is always confirmed with attending physician for finalization of assent waiver for the study before patient is approached. Assent will be obtained from the patient if he/she is at least 7 years of age and is alert enough or cognitively able to understand the nature of the study. This assent will be obtained for all child subjects (7-17 years old) and documented by signing a separate assent form (for 7- 13 years old) or by signing an assent line on the parent permission form (for 14-17 years old). If the patient turns 18 years old while still participating in the study, we will have patient confirm his or her interest in continuing participation. If patient is still interested in study participation we will have him or her consent during the current admission.

We plan to enroll only English speaking patients for this 20 patient pilot study. We do not have available funds and resources at this time to provide Spanish ICF documents for this pilot study. If we notice a large population of Spanish speaking patients being excluded we will consider including Spanish Speaking patients in the next phase of this study after the pilot is completed.

O. PROCEDURES TO BE EMPLOYED IN ANALYZING DATA AND THE ANTICIPATED SIGNIFICANCE OF THE PROPOSED STUDY

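### Adverse event follow-up after the same last dose can run from 7 to 30 days depending on when the catheter comes out, and the planned comparison between arms makes no allowance for this

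*Combined protocol and SAP*

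**What the plan says.** Section H sets the adverse event window as the active treatment period and then "for 30 days following the last dose of the t-PA/heparin, or for 7 days after CVC removal, whichever occurs first". Section J repeats the rule for any child who receives at least one dose. In both places the next sentence reads "For patients with CVC in place at time of hospital discharge, chart review will be performed to capture events up to 7 days after discharge". It does not say how it relates to the rule before it.

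Section D gives dosing "every 3 days until discharge from the PICU, CVC removal or a maximum of 10 doses received", so the date of the last dose itself depends on removal and PICU discharge.

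Section J also states that "At completion of the study adverse event rates between the study group and heparin control group will be compared". It does not define the rate or give a denominator. The statistical analysis plan in Section O names chi-square and Fisher's exact tests for categorical variables, and Mann-Whitney or t-tests for continuous or ordered ones. It mentions neither person-time nor unequal follow-up.

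The Serious Adverse Events paragraph of Section J has a separate rule: "Subjects whose treatment is discontinued will be followed for 30 days after the last t-PA/heparin control dose or until hospital discharge, whichever occurs first".

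**The concern.** Catheter removal and hospital discharge happen after randomisation, and the treatment could change when they occur. Dysfunction, CLABSI and VTE are trial outcomes and plausible reasons for taking a line out; that link is an inference, not a statement in the protocol. Section K says that "these complications result in unfavorable outcomes such as increased length of mechanical ventilation, increased length of stay", which ties the same outcomes to the date of discharge.

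If t-PA kept lines working longer, t-PA children could be watched longer and show more adverse events with no difference in harm. If it shortened stay among children who go home with a line, and the discharge sentence is a cut-off, they could be watched for less time. A comparison of simple proportions cannot separate harm from observation time in either case.

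The final comparison carries some weight because Section M plans no DSMB. No separate follow-up window is stated for clinical bleeding, CLABSI or VTE, and Section B intends to plan a multicentre trial from the rates found here.

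**Working it through.** The plan states no event rate or removal rate, so there is no figure to reproduce. The check applies the stated rules and then gives an illustration on assumed inputs.

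**1. Window after the last dose, by day of removal.** Let r be the number of days from last dose to removal. Sections H and J give window = min(30, r + 7).

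| r (days) | Window (days) |
|---|---|
| 0 | 7 |
| 3 | 10 |
| 7 | 14 |
| 14 | 21 |
| 23 or more | 30 |

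The range is 7 to 30 days, a ratio of 30/7 = 4.3. Dosing is every 3 days and stops at removal, so a child still on schedule who loses the line has about 7 to 10 days. A child whose dosing stopped at PICU discharge or after 10 doses, and who keeps the line, can have 30.

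**2. The discharge sentence.** Take a last dose on day 6 and the line still in place at discharge.
- Discharge on day 10: the general rule ends on day 6 + 30 = 36; the discharge sentence gives day 10 + 7 = 17.
- Discharge on day 40: the general rule still ends on day 36; the discharge sentence gives day 40 + 7 = 47.

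The sentence can therefore fall before or after the general end date, and the text does not say which governs.

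**3. Discontinued children.** Their rule is min(30, day of hospital discharge after last dose), which runs from 0 to 30 days with no 7-day tail.

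**4. Illustration.** Assumptions, none from the documents: a constant daily event hazard h, identical in both arms; a 7-day window in 30% of one arm and 70% of the other; 30 days for the rest. P(at least one event in t days) = 1 − exp(−h·t).

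Mean windows: 0.3 × 7 + 0.7 × 30 = 23.1 days, and 0.7 × 7 + 0.3 × 30 = 13.9 days.

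At h = 0.01, P(7) = 0.068 and P(30) = 0.259. The arms show 0.3 × 0.068 + 0.7 × 0.259 = 20.2% and 0.7 × 0.068 + 0.3 × 0.259 = 12.5%.

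| h per day | 30% early removal | 70% early removal | Both arms, fixed 30 days |
|---|---|---|---|
| 0.005 | 10.8% | 6.6% | 13.9% |
| 0.01 | 20.2% | 12.5% | 25.9% |
| 0.02 | 35.5% | 22.7% | 45.1% |

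The gap between arms comes from window length alone and vanishes with a fixed window.

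**5. What a fixed window leaves.** The treatment period still varies. With one lumen, a single dose gives 0 + 30 = 30 days in total. Ten doses every 3 days put the last on day 9 × 3 = 27, giving 27 + 30 = 57 days.

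**The case against.** Four stronger readings are tempting, and the documents do not support them.

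- **Collection stops at removal or discharge.** It does not under the general rule, which runs 7 days past removal with 30 days after last dose as an upper limit. Only the rule for discontinued subjects stops at hospital discharge.
- **One arm is observed for less time.** Unequal windows between children do not bias a randomised comparison unless window length differs by arm. No removal or discharge rates are given, and the argument can run in either direction.
- **The two sentences contradict each other.** The discharge sentence can be read as a specific method, chart review, for children who have gone home. It is ambiguous, not irreconcilable.
- **Late VTE or CLABSI after discharge is missed.** That follows only if the discharge sentence is a cut-off. Under the general rule, a child with the line still in is covered to day 30.

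The illustration has limits too. A constant hazard ignores any fall in catheter-related risk once the line is out, so it may overstate what a short window misses. This is a 20-child feasibility pilot sized by funding and time. Section H says a 2 mg systemic bolus of t-PA returns to endogenous levels within 30 minutes, so early drug-related bleeding would mostly fall inside a 7-day tail.

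These points narrow the concern but do not remove it. The window still depends on post-randomisation events, the discharge sentence is unclear, and no analysis allows for unequal time. The exposure is mainly in counts of all adverse events, later bleeding, CLABSI and VTE.

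**Conclusion.** The point holds in limited form, as an inexpensive improvement rather than a threat to the pilot. Observation after the same last dose ranges from 7 to 30 days according to catheter removal. Discharge adds to this if its sentence is a cut-off. That much follows from the text without assumptions.

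Bias in the comparison is conditional: it arises only if removal or discharge timing differs between arms. Its direction and size cannot be determined from the documents. The gap of 20.2% versus 12.5% shows how the mechanism would work on assumed hazards and removal shares; it is not an estimate for this trial.

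**What to change.** In Sections H and J:

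- Review the chart of every dosed child from first dose to 30 days after the last dose, regardless of CVC removal or discharge, and delete the clause that ends follow-up at the earlier of two dates.
- State that the discharge sentence describes the method of follow-up, not an earlier end date.
- Do not use the 7-day terms to lengthen or shorten the window for the between-arm comparison. Using them to extend it would recreate unequal follow-up in children who keep a line for a long time.
- Reconcile the sentence on discontinued subjects with this window.

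In Section O, count events from first dose to the end of that window. Compare arms as events per patient-day observed, alongside the proportion of children with an event. Both are needed because total observation would still run from about 30 to 57 days with one lumen.

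The cost is protocol wording and record review for some of 20 children: at most 30 − 7 = 23 extra days each under the general rule, and up to 30 for a discontinued child discharged on the day of the last dose. No visits or tests are added. Some of the extra events will be unrelated to treatment, and events treated at other hospitals may still be missed.

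### Section J counts any change from baseline as an adverse event and leaves the unit of the rate undefined, so the planned all-adverse-event comparison between arms is uninformative or mixes benign change with harm.

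*Combined protocol and SAP*

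**What the plan says.** The only definition of an adverse event is in Section J, under Adverse Event Monitoring: "Adverse events will be considered any change from baseline". It does not require the change to be unfavourable, and it gives no severity scale and no relatedness rule for non-serious events.

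The same paragraph commits the trial to a result: "At completion of the study adverse event rates between the study group and heparin control group will be compared", for inclusion in any final report. It does not say whether a rate is a proportion of subjects, a count per subject or a count per unit of time. Those followed are described as "Any patient receiving a minimum of 1 dose of the t-PA/heparin control". Follow-up ends 30 days after the last dose or 7 days after catheter removal, whichever is earlier.

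Nothing elsewhere narrows the definition. Section J says the expected events are in Section H, but Section H has only a narrative on bleeding risk and a paragraph on confidentiality. Section O (Statistical analysis plan) does not mention adverse events. It offers chi-square or Fisher tests for categorical variables and Mann-Whitney or t-tests for continuous or ordered ones.

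Two other provisions matter. Section O names clinical bleeding as a secondary outcome (Section D lists bleeding). Section J provides a causality discussion for any SAE, aggregate annual reporting of expected SAEs, and separate reporting of unexpected ones.

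**The concern.** A child in intensive care is expected to change. Extubation, a falling fever or a laboratory value returning to normal are all changes from baseline, and the sentence as written makes each an adverse event. Staff who follow it will log recovery together with harm. Staff who use their own judgement will be applying a rule that the protocol does not contain.

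At stake is the all-adverse-event comparison, which is the only planned between-arm look at non-serious harms other than the named secondary outcomes. If it is an incidence, it may be so close to its ceiling in both arms that no difference can appear. If it is a count, a difference could reflect more recovery as easily as more harm. One stated purpose of the pilot is to test the mechanics of a later multicenter trial, so a poor definition could be carried forward.

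**Working it through.** **Inputs from the documents.** Section E: "This single center, pilot study will enroll 20 subjects at CHW". Section D: "After 1:1 randomization", hence about 10 per arm. The size has no power calculation behind it (Section E: "This sample size was chosen for the ability to be internally funded"), so there is no figure of the plan's own to reproduce.

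**Assumptions.** Exactly 10 dosed subjects per arm; two-sided 0.05 (the plan states no alpha); background incidence of any change, and bleeding rates, as varied below.

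**Step 1: where the ceiling starts.** Suppose all 10 t-PA subjects have an event and *b* of 10 heparin subjects do. All 10 − *b* event-free subjects are then in one arm. With equal arms the two-sided Fisher p-value is 2 × C(10, 10 − *b*) / C(20, 10 − *b*), for *b* below 10.

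- *b* = 5: 2 × 252 / 15,504 = 0.033
- *b* = 6: 2 × 210 / 4,845 = 0.087
- *b* = 7: 2 × 120 / 1,140 = 0.21
- *b* = 9: 2 × 10 / 20 = 1.0

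So from 6 heparin subjects upward, no t-PA result is significant by Fisher. By uncorrected chi-square the threshold is 7: 10/10 v 6/10 gives p = 0.025, and 10/10 v 7/10 gives p = 0.060.

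**Step 2: how likely that is.** The chance that at least 6 of 10 heparin subjects have an event, by true background incidence:

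| Background | P(6 or more of 10) | Fisher power if t-PA is 100% |
|---|---|---|
| 50% | 0.38 | 62% |
| 70% | 0.85 | 15% |
| 80% | 0.97 | 3.3% |
| 90% | 0.998 | 0.2% |

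The two columns sum to one, because with t-PA at 100% the test rejects exactly when 5 or fewer heparin subjects have an event.

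**Step 3: dilution of a real harm.** Assume bleeding of 40% on t-PA and 10% on heparin, independent of a background *g* of any other change. Then P(any event) = 1 − (1 − *g*)(1 − bleeding).

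- *g* = 90%: 94.0% v 91.0%, Fisher power 0.05%
- *g* = 95%: 1 − 0.05 × 0.60 = 97.0% v 1 − 0.05 × 0.90 = 95.5%, power about 0.003%
- *g* = 99%: 99.4% v 99.1%, power effectively nil

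At *g* = 95%, 80% power would need about 2,518 per arm. Bleeding analysed alone would need 32 per arm.

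**Step 4: if the rate is a count.** Under a Poisson model with an assumed mean of 5 events per heparin subject, power is 58% for a ratio of 1.5 and 98% for a ratio of 2. This ignores overdispersion and so is optimistic. There is no ceiling, but under the present definition the count includes benign change, so a ratio above 1 would not by itself mean more harm.

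**Step 5: what a better definition cannot do.** For bleeding on its own with 10 per arm, Fisher needs at least 5/10 v 0/10 (p = 0.033) or 7/10 v 1/10 (p = 0.020). Power for 40% v 10% is 15%. Even 0/10 events leaves a two-sided exact 95% upper limit of 1 − 0.025^(1/10) = 31%.

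**The case against.** The strongest reply is that the harm of most interest is already analysed elsewhere. Bleeding is the only drug harm that Section H describes, and clinical bleeding is a secondary outcome with between-arm tests in Section O. A split of 5/10 v 0/10 would be seen there whatever the all-adverse-event table showed. SAEs also have their own review. This stands, and it limits the point to the all-adverse-event comparison. A reader might infer that the plan cannot show harm at all, or that its only safety comparison is lost; the documents do not support either.

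A second reply is that a rate need not be a proportion of subjects. This also stands: the ceiling belongs to one of two open readings. A reader might go further and infer that nearly every subject will have an event, so that the result is bound to be 10/10 v 10/10. That is plausible from the wording and the setting, but no incidence is given anywhere.

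A third reply is that a 20-subject feasibility pilot cannot settle safety under any wording. Step 5 agrees. That is a reason to present the safety results descriptively. It is no reason to keep a definition that counts recovery as harm, since the comparison will be reported whatever its power.

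Finally, an untoward-event definition could itself be met by most intensive-care patients. That is fair, and it is why the fix also asks for events by type and severity.

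**Conclusion.** The concern holds for one comparison. The stated definition is too broad as written, and the unit of the rate is missing. If the rate is the proportion of subjects with any event, the comparison cannot reach p ≤ 0.05 by Fisher once 6 of 10 heparin subjects have one, and power is 3.3% or less for backgrounds of 80% and above, even against 100% on t-PA. If the rate is a count, it is not capped but cannot be read as harm. These figures rest on 10 dosed subjects per arm, a two-sided 0.05 level and assumed backgrounds; the 50% row in Step 2 shows that the ceiling bites much less often if the background is moderate.

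The consequence is an uninformative or ambiguous adverse event comparison in the final report, and a definition unsuited to the later trial. Detection of bleeding through its own outcome and the individual review of SAEs are not affected. The trial's limited power for harm comes from its size, not from this sentence. The text should be changed because the correction is short and cheap.

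**What to change.** **Section J.** Define an adverse event as an untoward medical occurrence that is new or worsened from baseline after the first dose, whether or not related to study treatment. State the unit of the rate: subjects with at least one event, by type and severity, among those who received at least one dose.

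**Section O.** Alongside the existing clinical bleeding outcome, report the proportion of subjects with any SAE per arm. Give each a between-arm difference with an exact 95% confidence interval, and label the results descriptive.

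**Cost.** A few sentences in two sections, with no change to sample size, visits or follow-up. The small downside is that benign changes are no longer logged, which also lightens data entry. The change removes the ceiling caused by benign events but does not add power.
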